#### 8. DESCRIPTION OF STUDY TREATMENTS

### 8.1. Description of Treatments

In the Treatment Period, patients will be stratified by alopecia areata subtype and randomized to 1 of 2 CTP-543 treatment arms in a 1:1 ratio. Treatments arms will include:

- CTP-543 12 mg BID (1 x 12 mg and 1 x placebo tablet every 12 hours)
- CTP-543 24 mg QD (2 x 12 mg in the morning and 2 x placebo tablets in the evenings)

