### 8.3. Treatment Compliance

At each scheduled study visit after randomization, the Investigator or designee will interview the patient regarding treatment compliance and compare the number of dispensed versus returned study drug tablets. Patients should strive for 100% compliance with the daily dosing schedule. Retraining on treatment compliance should occur for patients with less than 80% or over 120% compliance at any visit and the Sponsor should be notified.

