### 8.4.2. Study Drug Packaging, Labeling, and Storage

CTP-543 active and placebo tablets will be packaged and labeled by an appropriately qualified vendor. Study drug will be dispensed at study visits as specified in the schedule of events (Table 1). To maintain the blind for investigators, subjects, and site personnel, subjects will take IP in the am and pm no matter which regimen they are assigned to:

- 12 mg BID (1 x 12 mg in AM + placebo; 1 x 12 mg in PM + placebo)
- 24 mg QD (2 x 12 mg QD in AM; 2 x placebo in PM)

Additional details on the packaging, labeling and dispensing instructions can be found in the Study Manual.

The label(s) for the investigational product will include sponsor name, address and telephone number, the protocol number, investigational product name, dosage form, amount of investigational product per container, lot number, unique dosing card number, storage conditions, and required caution statements and/or regulatory statements, as applicable. Additional information may be included on the label as applicable per local regulations.

Adequate supplies of study drug will be provided to each site. Study drug should be stored in the original package between 15°C to 25°C (59°F to 77°F), as stated on the product label, in a secure, temperature-monitored, locked area, under the responsibility of the Investigator or other authorized individual until dispensed to the patients.

Study drug dispensed to patients should be stored in the original package at room temperature as stated on the package label. No special handling procedures are required.

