Appendix 1 provides a description of the procedures planned at each visit.

3.2 Treatment Regimens

CTP-543 will be dosed orally as tablets. Doses and frequency will be allocated as follows:

- 12 mg BID CTP-543 (1 x 12 mg and 1 x placebo tablet every 12 hours)
- 24 mg QD CTP-543 (2 x 12 mg in the mornings and 2 x placebo tablets in the evenings)

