3.4 Changes to the Analysis from the Protocol

The Efficacy analysis population described in the synopsis of the protocol is referred to as the modified Intent-to-Treat (mITT) analysis population in Section 11.3 of the protocol. To avoid confusion, this analysis population will be called the mITT analysis population in this SAP as well as in the statistical outputs.

As per Section 11.4.3 of the protocol, the total number of days on study drug will exclude dose interruptions. However, dose interruptions will not be excluded from the duration of exposure to the study drug as specified in Section 11, in order to be in line with industry's standards.

	STATISTICAL ANALYSIS PLAN, Final v1.0
Protocol Number CP543.2003	Sponsor: Concert Pharmaceuticals, Inc.

As per Section 11.4.4 of the protocol, treatment-emergent AEs (TEAEs) are defined as any AE that occurs after administration of the first dose of study drug until Week 24 or Early Termination Visit. However, TEAEs will be defined as any AEs with onset date/time on or after the first dose of study drug (refer to Section 13.1), in order to be in line with the industry's standards.

As per Section 11.4.4 of the protocol, the number and percentage of patients with abnormal, clinically significant laboratory values (per Investigator judgment) will be summarized by dosing regimen for each clinical laboratory variable. This summary has been replaced by shift tables from Baseline to the worst post-Baseline result describing shifts to abnormality as assessed by the central laboratory (low, normal, high) (refer to Section 13.2). Abnormal, clinically significant laboratory values (per Investigator judgement) will be identified in by-patient data listing.

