11 STUDY TREATMENT EXPOSURE AND TREATMENT COMPLIANCE

A summary of exposure to study drug (days) will be presented by dosing regimen based on the Safety analysis population. Exposure to study drug, in days, will be computed as follows:

[(Date of last dose of study drug – Date of first dose of study drug) + 1]

Compliance with study drug (%) will be calculated as follow:

Number of tablets taken x 100%
Total number of tablets planned to be taken

where the number of tablets taken is defined as the total number of tablets dispensed minus the total number of tablets returned, and total number of tablets planned to be taken is defined as the exposure to study drug multiplied by the number of planned tablets per dose (i.e., 2).

Descriptive statistics for the compliance to study drug will be presented by dosing regimen based on the Safety population. Frequency distribution will also be presented for the following categories: < 80%, 80% - 120%, and > 120%.

Exposure and compliance will be displayed in a listing of study treatment administration.

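### SAP Section 11 divides tablets taken by half the scheduled number, so full adherence computes to 200% and true 80–120% adherence is reported as over 120%

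*SAP*

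**What the plan says.** SAP Section 11 calculates compliance as tablets taken over tablets planned, in percent.

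- **Tablets taken** is "the total number of tablets dispensed minus the total number of tablets returned". It is not restricted to active tablets.
- **Tablets planned** is "the exposure to study drug multiplied by the number of planned tablets per dose (i.e., 2").
- **Exposure** is in days, taken from dates: the bracketed difference "Date of last dose of study drug – Date of first dose of study drug) + 1".

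The result is summarised by arm with descriptive statistics and in three categories: below 80%, 80% to 120%, and above 120%.

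The regimens are consistent across the documents. SAP Section 3.2 gives "12 mg BID CTP-543 (1 x 12 mg and 1 x placebo tablet every 12 hours") for one arm. Protocol Section 8.1 gives "CTP-543 24 mg QD (2 x 12 mg in the morning and 2 x placebo tablets in the evenings") for the other, and Protocol Section 8.4.2 agrees: "24 mg QD (2 x 12 mg QD in AM; 2 x placebo in PM"). SAP Section 3.3 confirms that both arms take tablets morning and evening to keep the blind.

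Protocol Section 8.3 uses the same 80% and 120% limits and states what 100% refers to: "Patients should strive for 100% compliance with the daily dosing schedule".

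**The concern.** Days multiplied by tablets per dose is not a number of tablets unless there is one dose per day, and here there are two. The numerator accumulates at four tablets a day and the denominator at two, so the ratio is doubled. A value of 100% under the SAP then means half of the daily schedule, although the category limits are the protocol's and presume that 100% means all of it.

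At stake is whether the compliance table can be read as labelled. The trial compares two ways of giving the same total daily dose, and this table is the planned summary of whether patients took the scheduled tablets. A patient who skipped every evening dose would be listed as 100% compliant. In the once-daily arm the skipped tablets are all placebo; in the twice-daily arm they include half of the active drug. Meanwhile a patient who took everything would be listed as having taken twice the planned amount.

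**Working it through.** **Inputs**

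- Exposure E in calendar days: SAP Section 11.
- Numerator, all tablets dispensed minus returned: SAP Section 11.
- Tablets per dose, 2 in both arms (1 active + 1 placebo; or 2 active in the morning and 2 placebo in the evening): SAP Section 3.2, Protocol Sections 8.1 and 8.4.2.
- Doses per day, 2 in both arms: SAP Sections 3.2 and 3.3.
- Treatment period, 24 weeks × 7 = 168 days: SAP Section 3.1. This is nominal, since visits have a window of ±3 days.
- Categories below 80%, 80–120% and above 120%: SAP Section 11.

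**Step 1. Planned tablets as the SAP defines them.** E × 2 = 168 × 2 = 336.

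**Step 2. Planned tablets from the regimen.** E × doses per day × tablets per dose = 168 × 2 × 2 = 672 in each arm.

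**Step 3. Full adherence under the SAP formula.** 672 / 336 = 200%. E cancels, so the factor is 2 at any length of exposure: (4 × E) / (2 × E) = 2. If only the morning dose is taken on the last day, the result is 670 / 336 = 199.4%, which changes no category.

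**Step 4. Effect on the categories.** With true adherence a, the SAP value is a × 4E / 2E = 2a.

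| True adherence | SAP value | Category shown | Correct category |
|---|---|---|---|
| 39% | 78% | below 80% | below 80% |
| 40% | 80% | 80–120% | below 80% |
| 50% | 100% | 80–120% | below 80% |
| 60% | 120% | 80–120% | below 80% |
| 61% | 122% | above 120% | below 80% |
| 80% | 160% | above 120% | 80–120% |
| 100% | 200% | above 120% | 80–120% |
| 120% | 240% | above 120% | 80–120% |

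True adherence from 40% to 120% is put in the wrong category. Only values below 40% or above 120% keep the right one.

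**Step 5. The same bands in tablets at 168 days.**

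- Correct 80–120% band: 0.8 × 672 = 537.6 to 1.2 × 672 = 806.4.
- SAP 80–120% band: 0.8 × 336 = 268.8 to 1.2 × 336 = 403.2.

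The bands do not overlap, so a patient in the correct band cannot be reported in it.

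**Step 6. Readings that might rescue the formula.**

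- Exposure as a count of doses would give 672, but SAP Section 11 defines it in days from two dates.
- Counting active tablets only would give 2 per day in both arms, but the numerator counts all tablets, the text says per dose, and Protocol Section 8.4.1 defines study drug as CTP-543 or identical placebo.
- A deliberate change is not disclosed: SAP Section 3.4 lists the departures from the protocol and none concerns compliance.
- No other section supplies the missing factor.

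**The case against.** The strongest case against is about weight. Compliance is not an endpoint in Protocol Section 11.2 or SAP Section 2, no population definition in SAP Section 4 names it, and no SALT or safety analysis is said to use it. The factor is identical in both arms, so the ratio between arms is unaffected, and the continuous summaries can be recovered by halving. Values near 200% would be conspicuous, and SAP Appendix 2 requires outputs to be checked for accuracy and consistency. Site tablet counts under Protocol Section 8.3 are a separate check during conduct.

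All of this stands and limits the consequence. It does not make the definition right. Validation against a wrong specification can pass, and correcting the program without correcting the text would be an undocumented departure from the SAP. The category counts cannot be recovered by halving; they have to be rebuilt from the listing.

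A second point is that the claim about every patient depends on measuring adherence over the SAP's exposure days, interruptions included. Judged only on uninterrupted days, a patient at 80% with 42 interruption days in 168 computes to 0.8 × 4 × 126 / 336 = 120% and falls in the middle category. Protocol Section 8.2 allows for more than one interruption, so this can happen, but it is an edge case and depends on a different definition of adherence from the SAP's own.

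**Conclusion.** The concern holds. The compliance denominator in SAP Section 11 is half of what the regimens require, so every computed value is twice the true one. The means, standard deviations and between-arm differences in percentage points are all doubled, and the category table is wrong for true adherence anywhere from 40% to 120%. The tablet counts rest on a nominal 168 days; the factor of 2 does not depend on that. The statement that all true 80–120% values land above 120% assumes adherence is measured over the same exposure days as the SAP uses. The damage is confined to the compliance statistics, category table and listing, and favours neither arm. It should be corrected, but it does not bear on the efficacy or safety conclusions.

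**What to change.** In SAP Section 11, define planned tablets as exposure in days × 2 doses per day × 2 tablets per dose, that is, four per day in both arms. Full adherence then gives 672 / 672 = 100%, and the existing three categories can stay, because they again match the limits in Protocol Section 8.3. The cost is one line of text and one constant in the derivation program; no new data are needed.

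One further sentence is optional. SAP Section 3.4 says that "dose interruptions will not be excluded from the duration of exposure to the study drug", and the formula carries those days into planned tablets, but the section does not mention compliance. The SAP could say whether that is intended. With the corrected denominator, one 21-day interruption in an otherwise adherent patient gives (168 − 21) / 168 = 87.5%. The value drops below 80% only if (E − 21) / E < 0.80, that is, if exposure is under 105 days. The main correction does not depend on this choice.

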12 EFFICACY ANALYSIS

12.1 Primary Efficacy Endpoint Analysis

The primary efficacy endpoint is the relative change from baseline in SALT score at Week 24. The SALT is a measure of hair absence that quantifies the amount of scalp surface without hair in a pre-specified quadrant of the scalp (right side [RRS], top [TRS], left side [LRS], and back [BRS]), that is further summed after applying a quadrant-specific multiplier indicative of scalp surface area contribution, to provide an overall score of total hair loss:

Total SALT Score =
$$(LRS * 0.18) + (RRS * 0.18) + (TRS * 0.40) + (BRS * 0.24)$$

Refer to Section 6.2 for an important note about SALT absolute change from Baseline and relative change from Baseline endpoint definitions

Relative change in SALT score from Baseline to Week 24 will be summarized descriptively based on the mITT analysis population by dosing regimen. Difference of the means between the two

	STATISTICAL ANALYSIS PLAN, Final v1.0
Protocol Number CP543.2003	Sponsor: Concert Pharmaceuticals, Inc.

dosing regimens will also be provided along with a two-sided 90% Confidence Interval (CI). SALT data will be displayed in a by-subject data listing.

Line plots of means (+/- standard error of the mean [SEM]) SALT score over time by dosing regimen will be presented. Similar, line plots of means (+/- SEM) absolute change in SALT score and relative change from Baseline in SALT score over time by dosing regimen will also be provided.

Supportive Analysis

If applicable (refer to Section 4.2), the primary efficacy analysis will be repeated based on the PP analysis population.

Subgroup Analyses

Subgroup analyses by Baseline alopecia areata subtype (refer to Section 8 for the definition of Baseline alopecia areata subtype) will be performed.

12.2 Secondary Efficacy Endpoint Analyses

12.2.1 Responder Analysis: Proportion of patients achieving at least a 90%, 75%, and 50% in relative change from Baseline in SALT score at Weeks 4, 8, 12, 16, 20, and 24

For the proportion of patients achieving at least a 90%, 75%, and 50% relative change from Baseline in SALT score at Weeks 4, 8, 12, 16, 20, and 24, frequency and proportion will be presented by dosing regimen based on the mITT analysis population. The difference in proportions along with the two-sided Wald 90% CI (using the binomial approximation with a Wald continuity correction) will also be provided at each visit.

Additionally, line plots of proportions of patients over time by dosing regimen will be presented for the proportion of subjects achieving ate least a 50% in relative change from baseline only.

The same supportive and subgroup analyses as for the primary efficacy endpoint will be performed for this secondary efficacy endpoint (refer to Section 12.1).

12.2.2 Absolute change in SALT score from Baseline to Weeks 4, 8, 12, 16, 20, and 24, and relative change in SALT score from Baseline to Weeks 4, 8, 12, 16, and 20

For the absolute change in SALT score from Baseline to Weeks 4, 8, 12, 16, 20, and 24 as well as the relative change in SALT score from Baseline to Weeks 4, 8, 12, 16, and 20, a similar analysis approach as outlined for the primary efficacy endpoint (refer to Section 12.1) will be used, including the supportive and subgroup analyses.

	STATISTICAL ANALYSIS PLAN, Final v1.0
Protocol Number CP543.2003	Sponsor: Concert Pharmaceuticals, Inc.

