#### **Dosing Regimen and Dose Selection Rationale**

Analyses suggest that across acute and chronic disease states, reducing dosage frequency from multiple dosing to QD dosing may improve adherence to therapies among patients, and may result in subsequent decreases in health care costs (Srivastava, 2013). Therefore, Concert will explore further the tolerability and efficacy of BID versus QD dosing with CTP-543.

The selection of the 12 mg BID and 24 mg QD dose of CTP-543 for this study is supported by the safety data of CTP-543 observed in the multiple ascending dose (MAD) study in healthy volunteers as well as safety and efficacy data from an ongoing Phase 2 study in patients with moderate to severe AA.

In the MAD study, doses of CTP-543 up to 16 mg BID and 32 mg QD were administered for 7 consecutive days and appeared to be generally well-tolerated. The MAD study, along with the preclinical safety package for the compound, supported the advancement of CTP-543 into an initial Phase 2 clinical trial in patients with AA (CP543.2001).

CP543.2001 was designed as a sequential, double blind, placebo-controlled, Phase 2 study to assess CTP-543 at 4 mg BID and 8 mg BID compared to placebo over 24-weeks of dosing. Each dosage strength was assessed sequentially and interim efficacy and safety results have been reported for the 4 mg BID and 8 mg BID cohorts.

The primary efficacy endpoint in the 8 mg twice-daily cohort was met with 47% of patients achieving a  $\geq$  50% reduction in their overall SALT score from baseline compared to placebo (p<0.001). In the 4 mg twice-daily cohort there was a 21% response; however, this was not significantly different from placebo.

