#### **11.4.2.** Efficacy

For the primary efficacy endpoint and other continuous measures, the confidence interval(s) for the dosing regimen difference at Week 24 will be calculated. For categorical measures (e.g. proportion of responders), the confidence interval(s) for the dosing regimen difference at Week 24 will be calculated based on normal approximation for the binomial distribution, using the Wald continuity correction [(1/n1 + 1/n2/2]].

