3 STUDY DESIGN

3.1 Overall Design

This is a randomized, parallel-group, multicenter study to evaluate the efficacy and tolerability of two dosing regimens of CTP-543 (12 mg twice daily [BID] vs 24 mg once daily [QD]) in adult patients with chronic, moderate to severe alopecia areata. Patients will be between 18 and 65 years of age and experiencing an episode of alopecia areata lasting at least 6 months and not exceeding 10 years, with at least 50% hair loss as measured by the Severity of Alopecia Tool (SALT) at Screening and Baseline, and are not concurrently being treated for alopecia areata with other treatments that might affect hair regrowth or immune response. Up to approximately 75% of alopecia areata patients with alopecia totalis or universalis, and no more than 10% of patients with alopecia ophiasis will be enrolled.

A full list of the inclusion and exclusion criteria can be found in Sections 7.1 and 7.2 in the CP543.2003 Protocol.

Patients may be screened up to 28 days prior to initiation of study drug. The Treatment Period is a 24-week dosing period where patients will be randomized to receive either 12 mg BID or 24 mg OD of CTP-543.

[figure not shown]
[figure not shown]

Figure 1: Study Design

Patients will provide informed consent prior to completing any screening procedures. Patients meeting screening criteria will continue to the Day 1 Randomization Visit for review of eligibility and Baseline assessments. Patients meeting all eligibility criteria will be randomized to receive either 12 mg BID CTP-543 or 24 mg QD CTP-543 in a 1:1 ratio. Approximately 60 patients are planned to be randomized in the study (i.e., approximately 30 patients per dosing regimen).

Patients will take the first dose of study drug in the clinic on Day 1 and will be instructed to take study drug every 12 hours. To minimize the bias in the evaluation of study endpoints, patients, investigators, and site personnel will be unaware of the active drug dosing regimen by administering 2 x 12 mg tablets and 2 x placebo tablets 12 hours apart from each other for the 24 mg QD study drug. Patients should dose study drug in the clinic on all Study Visit Days after clinical laboratory blood draws are completed.

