6.9 Examination of Subgroups

The analysis of the primary and secondary efficacy endpoints will be repeated for the following subgroups (refer to Section 8 for the definition of each alopecia areata subtype):

- Subjects with alopecia areata at Baseline;
- Subjects with alopecia totalis or alopecia universalis at Baseline;
- Subjects with alopecia ophiasis at Baseline

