12.4 Other Efficacy Endpoint Analyses

12.4.1 Responder Analysis: Proportion of patients achieving at least 80% in relative change from Baseline in SALT score at Weeks 4, 8, 12, 16, 20, and 24

The proportion of patients achieving at least 80% in relative change from Baseline in SALT score at Weeks 4, 8, 12, 16, 20, and 24, frequency and proportion will be summarized and analyzed similarly to the proportion of patients achieving at least a 90%, 75%, and 50% relative change from Baseline in SALT score at Weeks 4, 8, 12, 16, 20, and 24 (refer to Section 12.2.1).

12.4.2 Proportion of Subjects with a SALT Score ≤ 10 and ≤ 20 at Weeks 12 and 24

The number and percentage of subjects with a SALT score ≤ 10 and ≤ 20 at Weeks 12 and 24 will be summarized based on the mITT analysis population by visit and dosing regimen. The difference in percentages along with the two-sided Wald 90% CI will also be provided at each visit.

No supportive and subgroup analyses will be performed for this endpoint.

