12.5 Summary of Efficacy Endpoint Analyses

Efficacy Endpoint	Collection Time	Method
Primary		
Relative change from Baseline in SALT score to	Baseline and Week 24	Descriptive statistics by visit and dosing regimen with difference in means and two-sided 90% CI (t-distribution) for each post-baseline visit
Week 24		 Main analysis: using LOCF imputation based on mITT analysis population
		 Supportive analysis: using LOCF imputation based on PP analysis population, if applicable
		 Subgroup analyses: using LOCF imputation based on mITT analysis population within each subtype of alopecia areata at Baseline
Secondary		
Responder (90%, 75% and 50%) in relative change from Baseline in SALT	Baseline and Weeks 4, 8, 12, 16, 20, and 24	Count and proportion of subjects by visit and dosing regimen for each responder definition separately with difference in proportions and two-sided Wald 90% CI for each post-baseline visit
score at Weeks 4, 8, 12, 16, 20, and 24	6,	 Main analysis: using LOCF imputation based on mITT analysis population
		 Supportive analysis: using LOCF imputation based on PP analysis population, if applicable
		 Subgroup analyses: using LOCF imputation based on mITT analysis population within each subtype of alopecia areata at Baseline

	STATISTICAL ANALYSIS PLAN, Final v1.0
Protocol Number CP543.2003	Sponsor: Concert Pharmaceuticals, Inc.

Efficacy Endpoint	Collection Time	Method
Absolute change from Baseline in SALT score to	Baseline and Week 4, 8, 12, 16, 20, and 24	Descriptive statistics by visit and dosing regimen with difference in means and two-sided 90% CI (t-distribution) for each post-baseline visit
Weeks 4, 8, 12, 16, 20, and 24		 Main analysis: using LOCF imputation based on mITT analysis population
		 Supportive analysis: using LOCF imputation based on PP analysis population, if applicable
		 Subgroup analyses: using LOCF imputation based on mITT analysis population within each subtype of alopecia areata at Baseline
Relative change from Baseline in SALT score to Weeks 4, 8, 12, 16, and 20 Baseline and Week 4, 8, 12, 16, and 20	· · · · · · · · · · · · · · · · · · ·	Descriptive statistics by visit and dosing regimen with difference in means and two-sided 90% CI (t-distribution) for each post-baseline visit
		 Main analysis: using LOCF imputation based on mITT analysis population
	 Supportive analysis: using LOCF imputation based on PP analysis population, if applicable 	

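### The continuity-corrected Wald 90% interval for responder differences is about as wide as a 95% score interval at mid-range rates, and in the ophiasis subgroup it often gives impossible limits

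*SAP*

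**What the plan says.** SAP 12.2.1 covers responders at the 50%, 75% and 90% thresholds at Weeks 4 to 24. The difference between regimens is given "along with the two-sided Wald 90% CI (using the binomial approximation with a Wald continuity correction) will also be provided at each visit", and the analysis is repeated by alopecia subtype. SAP 12.4.1 extends the method to the 80% threshold by reference. SAP 6.9 lists "Subjects with alopecia ophiasis at Baseline" as one of the three subgroups, while SAP 3.1 says that "no more than 10% of patients with alopecia ophiasis will be enrolled".

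The method comes from Protocol 11.4.2: "For categorical measures (e.g. proportion of responders), the confidence interval(s) for the dosing regimen difference at Week 24 will be calculated" from a normal approximation, "using the Wald continuity correction [(1/n1 + 1/n2/2" (the brackets in the printed formula do not balance). SAP 12.4.2, on SALT scores of at most 10 and at most 20, says only: "The difference in percentages along with the two-sided Wald 90% CI will also be provided at each visit". The SAP 12.5 table uses the same short label for the responder endpoints: "for each responder definition separately with difference in proportions and two-sided Wald 90% CI for each post-baseline visit".

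Neither document gives a truncation rule, a minimum subgroup size or a small-sample alternative.

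**The concern.** Protocol 11.4 says that efficacy comparisons serve estimation and that no formal testing is done. A reader will therefore take the 90% label literally. The correction adds a fixed amount to each side of the interval, which matters with about 30 patients per arm and dominates with about three. Three things are at stake:

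- Week 24 responder results would look less precise than the data allow.
- The ophiasis table would contain limits that no difference in proportions can take.
- At very low rates the error can reverse, and the interval becomes too narrow.

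A smaller point is that the wording leaves some room for two programmers to treat the SALT ≤10 and ≤20 intervals differently.

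**Working it through.** **Inputs**
- About 60 patients randomized 1:1, so about 30 per arm (SAP 3.1, 3.3). SALT endpoints use LOCF on the mITT population, so the analysed number should be nearer 30 than the 25 completers of SAP 6.1.
- Two-sided 90%, z = 1.645 (SAP 6.4).
- Week 24 rates for the 50% threshold in the earlier study: 47% at 8 mg BID and 21% at 4 mg BID (Protocol 4.2.1). The documents give no rate for 12 mg BID or 24 mg QD, so these are assumed as a plausible range.
- Ophiasis: 10% of 60 = 6 patients at most, about 3 per arm.

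The plan states no expected width or coverage for responder intervals, so there is no figure of its own to reproduce.

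**Planned interval**

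p1 − p2 ± [1.645 × √(p1q1/n1 + p2q2/n2) + (1/n1 + 1/n2)/2]

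This reads the Protocol's correction as half the sum of the reciprocals. Read literally as 1/n1 + 1/n2/2, it would be wider still: 0.525 against 0.491 at 50% and 30 per arm.

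**One result by hand: 14/30 versus 14/30**
- Standard error = √(2 × 0.4667 × 0.5333/30) = 0.1288
- 1.645 × 0.1288 = 0.212, and the correction is (1/30 + 1/30)/2 = 0.033
- Half-width 0.245, width 0.490
- Miettinen-Nurminen (MN) widths for the same table: 0.418 at 90% and 0.494 at 95%
- 0.490/0.418 = 1.17, so the planned interval is 17% wider than the 90% score interval and almost equals the 95% one

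**Exact coverage and mean width, 30 per arm**, summing over all outcomes of two independent binomials:

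| True rates | Planned: coverage, width (points) | MN 90%: coverage, width (points) |
|---|---|---|
| 47% and 47% | 94.6%, 48.3 | 90.8%, 41.2 |
| 21% and 21% | 93.9%, 40.5 | 89.2%, 34.8 |
| 47% and 21% | 94.3%, 44.6 | 89.7%, 37.9 |

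At 47% in both arms, Newcombe's interval gives 90.8% and 40.0 points. A 95% MN interval averages 48.7 points. A 90% MN interval with only 21 per arm averages 48.6 points. Over a grid of 20% to 80% in each arm, the planned interval averages 93.7% coverage (92.6% to 94.8%) and MN 90.0% (88.0% to 92.2%).

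**Low rates** (assumed; the documents give none for early visits). On a 1% to 15% grid the planned interval averages 95.7% and falls below 90% at 2.7% of points. The exceptions come from the 0/30 versus 0/30 table. There the standard error is zero and only the correction remains, giving ±3.3 points (MN ±8.4). With true rates of 5% and 0%, that table occurs with probability 0.95³⁰ = 0.215 and its interval misses the true 5-point difference. Coverage is therefore 78.5% (MN 98.4%).

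**Ophiasis, 3 versus 3.** Every table with unequal counts, 12 of 16, puts a limit beyond ±100 points. Without the correction it would be 4 of 16.
- 3/3 versus 0/3: standard error 0, correction (1/3 + 1/3)/2 = 0.333, interval 67% to 133% (MN 30% to 100%).
- 2/3 versus 1/3: −63% to 130%.
- Chance of an impossible limit = 1 − P(equal counts). At a 47% rate, the probabilities of 0, 1, 2 and 3 responders are 0.149, 0.396, 0.351 and 0.104. Their squares sum to 0.313, so the chance is 69%. It is 59% at 21%, 41% at 10% and 25% at 5%.
- With a 2 versus 4 split, 11 of 15 tables are affected.

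**The case against.** The best case for leaving the plan alone is that the method is prespecified in the Protocol, named openly, and mostly errs on the safe side.

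- **The coverage contrast depends on n.** At 47% in both arms it is 94.6% versus 90.8% with 30 per arm, but 91.9% versus 91.5% with 28, and 93.6% versus 88.2% with 25. On the 20% to 80% grid the planned interval stays above 90%, while MN falls as low as 88.0%. This stands: MN is not exact. The excess width, however, does not depend on a favourable n. At 12/25 versus 12/25 it is 0.545 against 0.457, or 19%. In a trial with no tests, over-coverage protects no error rate and only overstates uncertainty.
- **No decision rests on these intervals.** True. They concern secondary and other endpoints, counts and proportions appear beside them, and point estimates are unchanged. This limits the severity.
- **The ophiasis count treats all tables as equally likely, and three per arm is a ceiling.** Also true. At rates of 10% or lower, impossible limits are the minority outcome. A score interval at that size is nearly uninformative too, which argues for printing no interval there.
- **The 5% versus 0% example is a boundary case.** It is: coverage is 83.8% at 5% versus 1% and 99.3% at 5% versus 2%.
- **The short label in SAP 12.4.2 is probably shorthand.** Likely so. SAP 12.5 uses the same label for endpoints that SAP 12.2.1 explicitly corrects, Protocol 11.4.2 applies the correction to categorical measures generally, and SAP 3.4 lists no departure. The ambiguity is minor.

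**Conclusion.** The concern holds. For mid-range responder rates and about 30 patients per arm, the planned interval is roughly 17% to 20% wider than a 90% score interval. That is the precision a score interval would give with about 21 per arm. The result rests on responder rates in the region of the earlier study's 21% to 47%, which come from other doses, and on reading the correction as half the sum of the reciprocals.

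In ophiasis, at the 3 versus 3 ceiling, three quarters of possible tables give an impossible limit. The chance is 69% at a 47% rate and 41% at an assumed 10%. The opposite error, an interval that is too narrow, is confined to one arm having almost no responders.

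If the correction were left out for SALT ≤10 and ≤20, a 0 versus 0 result at Week 12 or 24 would give an interval of zero width. The primary t-based interval is not affected. This is a change that should be made, not one on which the trial's conclusions turn.

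**What to change.** Use one identical sentence in SAP 12.2.1, 12.4.1, 12.4.2 and 12.5: *The difference in proportions with its two-sided 90% Miettinen-Nurminen score CI will be provided at each visit.* Newcombe's interval would also be acceptable. For the ophiasis subgroup, present counts and proportions with no interval. Enter the departure from Protocol 11.4.2 in SAP 3.4, which already lists other changes from the Protocol.

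If the sponsor prefers to keep the Wald interval, the SAP should at least write out the correction with balanced brackets, state in 12.4.2 and 12.5 that it applies, and drop the ophiasis interval.

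The cost is wording in four SAP sections, one entry in 3.4 and a different option on the SAS PROC FREQ risk-difference request. No new data are needed. The downsides are a documented change from the Protocol method and coverage slightly below 90% in places: for MN, 88.0% at lowest on the 20% to 80% grid and 87.4% on the 1% to 15% grid with 30 per arm; for both score methods, 88.2% at a 47% rate with 25 per arm.
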